Title: The Impact of Free Fatty Acid Reduction on Vascular Function in the Metabolic Syndrome

NCT00759291

Document Date: February 28, 2008

STUDY PROCEDURES AND PROTOCOL

This study uses a randomized, placebo-controlled crossover design.

After providing informed consent, both groups will undergo an initial screening visit in the Vascular Medicine Research Center. This visit will include a comprehensive health history and physical exam and anthropomorphic data collection (height, weight, body mass index (BMI) and waist-hip ratio). Screening blood tests will be drawn to assess fasting glucose, blood count, lipid profile, glycosylated hemoglobin, and assessment of renal and hepatic function. Baseline serum insulin and nonesterified free fatty acid levels will also be drawn at this visit. An ECG will be performed.

We hypothesize that acipimox, by decreasing plasma FFA concentrations, will augment endothelium-dependent vasodilation in conduit vessels and insulin-mediated vasodilation in forearm resistance arterioles *in vivo*, whole-body insulin sensitivity, and AKT and eNOS phosphorylation in skin biopsy specimens *ex vivo*, when compared with placebo.

Subjects will be studied at 2 separate visits, 4 weeks apart, in a randomized, double-blind crossover design. Subjects will receive either acipimox 250 mg tablets orally every 6 hours, or matching placebo, for 7 days prior to and at 7 am on the morning of the study visit. Each visit will include vascular function testing and a forearm skin biopsy. Forearm blood flow will be measured in the basal state, and with insulin infusion.

Evaluation of vascular function in conduit vessels:

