Immunodetection: Serial 4 µM sections of skin biopsy sections are deparaffinized, hydrated, and serially incubated in citrate buffer, H₂O₂, blocking solution, primary antibody, and appropriate secondary antibody, with intervening washes. The ABC biotin/avidin method with Nova Red substrate is utilized for immunodetection (Vector Labs). Primary antibodies include: total Akt (Cell Signaling), phospho-specific Akt (Ser 473, Cell Signaling), total eNOS (Transduction Labs), and phospho-specific eNOS (Ser 1177, Cell Signaling). When available, blocking peptide is incubated with primary antibody in a separate section to ensure specificity of staining. If blocking peptide is not available, additional sections are incubated without primary antibody. To ensure localization of identified signal in vascular cells, additional sections will be processed for immunofluorescence and colocalization with primary antibodies directed against the endothelium-specific von Willebrand factor (Santa Cruz Biotechnology). Images will be viewed using an AX70 Olympus Microscope with Phase 3 Imaging System (Image Pro 4.0 software) or the Zeiss LSM-410 Invert Laser Scan confocal microscope with imaging software (Matrox Image-Series Utilities).

Assays for markers of inflammation, insulin, free fatty acids

Plasma samples from insulin resistant and healthy subjects will be assayed for high sensitivity CRP (hsCRP), tumor necrosis factor-α (TNF-α), and interleukin-6 (IL-6) using the respective ELISA kits (Sigma; Endogen, Woburn, MA; BenderMedSystems; Vienna, Austria). Plasma insulin concentration will be measured using an Immunoenzymatic Sandwich Assay (Beckman Coulter, Inc.). Acrylodan-labeled Intestinal Fatty Acid Binding Protein (ADIFAB), a fluorescent molecule, will be used to assay the concentration of free fatty acids. The assay is accurate to about 1nM (72). All assays will be performed in duplicate by investigators blinded to the status of the subject (metabolic syndrome or control) and treatment.

BIOSTATISTICAL ANALYSIS

Statistical Analysis

Sample size calculation: All specified protocols employ a randomized, placebo-control cross-over design. Given the paired-design, the sample sizes have been calculated using estimates of the difference in flow-mediated, endothelium-dependent vasodilation after placebo and active treatment.

Table 2: Calculated Power For a Given Effect Size and Standard Deviation
Standard Deviation

Treatment Effect	3.5%	4.0%	4.5%
2.5%	.97	.91	.84

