3.0%	.99	.98	.94
3.5%	1.0	.99	.98

endothelium-dependent vasodilation (i.e., the change in brachial artery vasodilation) between active therapy and placebo, will be assessed using repeated measures ANOVA (73). All analyses will employ the intention-to-treat principle. The treatment “order effect” will be explored by examining the interaction between treatment group (e.g. acipimox vs. placebo) and sequence of treatment (placebo first vs. active therapy first).

Baseline characteristics of treatment and control patients will be compared using Student’s t-test or non-parametric tests, depending on the distribution of the data. To examine whether the active therapy has similar effects on flow-mediated vasodilation between healthy subjects and those with the metabolic syndrome, we will test the interaction between treatment group and the metabolic syndrome (yes/no). In secondary analyses, we will assess the effects of active therapy on eNOS phosphorylation, insulin sensitivity, and plasma inflammatory markers such as CRP, IL-6, and TNF- α . We will assess the relationship between the change in eNOS phosphorylation and changes in endothelium-dependent vasodilation using linear regression analyses, controlling for age, and gender. Likewise, we will examine the relationship between changes in insulin-mediated vasodilation and insulin-sensitivity associated with active treatment. Multiple analysis of variance (MANOVA) will be used to examine the main and interaction effects of categorical variables on multiple dependent variables, and multiple analysis of covariance (MANCOVA) for continuous independents. Thus, in the analyses, we can include vascular function and other outcomes simultaneously as dependent variables in the models. If the dependent variables are uncorrelated with each other, repeated measure ANOVA for each dependent variable will be employed.

Data interpretation: Vascular function will be determined after each intervention. Each intervention will be studied individually. If flow-mediated vasodilation is restored after an intervention (acipimox) compared with placebo, it will be interpreted that FFA impairs endothelial insulin signaling and decreases endothelium-dependent vasodilation. This interpretation will be confirmed by cutaneous tissue testing. If eNOS serine₁₁₇₇ phosphorylation is increased after an intervention compared to placebo, it will be interpreted that improved activation of the PI3-kinase

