Based on previous studies, we expect to find an absolute difference in flow-mediated, endothelium-dependent vasodilation of the brachial artery between the test agent and placebo of 3% with an estimated standard deviation of 4% (68). With a 2-sided alpha error of 0.05 and a power of 90%, 30 subjects in each group of each protocol should find at least this difference in the primary endpoint (Table 2).

Statistical methods: All descriptive data will be expressed as means \pm standard deviation. The primary endpoint of change in flow-mediated,

pathway increases eNOS phosphorylation and resultant NO production. This interpretation will be supported if multivariate linear regression analysis defines a significant positive relationship between changes in eNOS phosphorylation and vascular and/or skeletal muscle metabolic function. If endothelium-dependent (flow-mediated) or insulin-mediated vasodilation remains similar despite an intervention (acipimox), it will be interpreted as a lack of effect of the agent on endothelial-insulin signaling and vascular function. If any intervention increases vasodilation to nitroglycerin, it will be interpreted that the intervention has improved vascular smooth muscle function. If the intervention improves vascular function in both subjects with the metabolic syndrome and healthy subjects, this will be interpreted as a generalized effect, independent of the metabolic syndrome.

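### The rule that calls the eNOS/NO mechanism supported does not require a mean gain in function, and it can contradict the plan's own lack-of-effect rule

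*Combined protocol and SAP*

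**What the plan says.** The protocol is a two-period crossover: "Subjects will be studied at 2 separate visits, 4 weeks apart, in a randomized, double-blind crossover design". Each subject therefore supplies one acipimox-minus-placebo change per measure.

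Three parts of the Biostatistical Analysis section bear on the mechanism.

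- **Statistical methods** plans to assess the "relationship between the change in eNOS phosphorylation and changes in endothelium-dependent vasodilation using linear regression analyses, controlling for age, and gender". No treatment, sequence or group term is named for this model.
- **Data interpretation, eNOS rule.** If eNOS phosphorylation is higher after the intervention than after placebo, this is taken to mean that PI3-kinase activation raised eNOS phosphorylation and, with it, NO production. That interpretation counts as supported if "multivariate linear regression analysis defines a significant positive relationship between changes in eNOS phosphorylation and vascular and/or skeletal muscle metabolic function". The only condition on a mean is the one on eNOS.
- **Data interpretation, next rule.** If flow-mediated or insulin-mediated vasodilation stays similar despite acipimox, the conclusion is that the agent had no effect on endothelial-insulin signaling or on vascular function.

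The plan does not say which rule prevails when both apply.

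**The concern.** The support rule is about what acipimox does, but the p-value it uses does not respond to what acipimox does on average. The slope asks whether subjects whose eNOS differed more between the two visits also differed more in function. Ordinary visit-to-visit covariation of two measures taken at the same visit could make it positive with no drug effect on function.

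At stake is a reported conclusion. With eNOS up, FMD flat and a positive slope, one set of data meets both the condition for a supported mechanism and the condition for no effect on signaling. With FMD worse on acipimox, the support rule can still be met, and the lack-of-effect rule, written for unchanged vasodilation, does not clearly apply.

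**Working it through.** **1. The plan's own figure.** Sample size calculation expects an FMD difference "between the test agent and placebo of 3% with an estimated standard deviation of 4" per cent, with 30 subjects per group and two-sided alpha 0.05. For a paired t-test the noncentrality is (3/4) × √30 = 4.108 on 29 degrees of freedom, which gives power 0.978; Table 2 has .98. All nine cells of Table 2 reproduce within 0.01 in this way. So the 4% acts as the SD of the within-subject difference, and it is used as such below.

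**2. The slope ignores shared shifts.** Let x be the eNOS change and y the FMD change. The fitted slope is

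b = Σ x̃ỹ / Σ x̃²,

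where x̃ and ỹ are residuals after regression on the intercept, age and gender. Adding a constant c to every x and d to every y leaves the residuals, and so b, its standard error and its p-value, unchanged. Only the intercept moves, by d − bc. In one simulated data set:

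| added to eNOS, FMD | slope | p | intercept |
|---|---|---|---|
| 0, 0 | 1.7843 | 0.00168 | −7.9255 |
| 0.75, 0 | 1.7843 | 0.00168 | −9.2638 |
| 0.75, 3 | 1.7843 | 0.00168 | −6.2638 |
| 5, 10 | 1.7843 | 0.00168 | −6.8472 |

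Check on the third row: −7.9255 + 3 − 1.7843 × 0.75 = −6.264. (Age is not centred here, so the intercept has no direct meaning; only its movement matters.)

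**3. The two rules side by side.** Take eNOS increased, slope significantly positive, mean FMD unchanged. The eNOS rule returns mechanism supported. The next rule returns no effect on endothelial-insulin signaling or vascular function. No correlation has to be assumed to see this.

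**4. How often the support rule is met with no FMD effect.** Inputs: FMD change SD 4% (from the plan), true mean FMD change 0. Assumed, because the plan gives no figures: a mean eNOS rise of 0.75 SD of its paired difference, and a correlation r between the two changes from visit-to-visit variation alone. The model includes age and gender; tests are two-sided at 5%, counted in the positive direction.

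| r | 0 | 0.2 | 0.3 | 0.4 | 0.5 |
|---|---|---|---|---|---|
| eNOS up and slope positive, n = 30 | 2% | 17% | 34% | 56% | 78% |
| same, both groups pooled, n = 60 | 2% | 32% | 64% | 89% | 98% |

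Separate simulation runs agree within about 2 points. A hand check for r = 0.4, n = 30 uses Fisher's z: atanh(0.4) = 0.424, standard error 1/√(30 − 2 − 3) = 0.2, ratio 2.12, so P(slope positive) ≈ Φ(2.12 − 1.96) = 0.56. The eNOS condition has power 0.978, because 0.75 SD is the same standardised effect as 3/4 in step 1. The product is about 0.55.

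With true FMD 2 points worse on acipimox and r = 0.4, the rates are about 56% (n = 30) and 89% (n = 60), the same as at zero effect, as step 2 implies.

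**5. Adding a condition on mean function.** At r = 0.4:

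| true FMD effect | n | as written | with mean FMD gain required |
|---|---|---|---|
| 0 | 30 | 56% | 1% |
| 0 | 60 | 89% | 2% |
| +3% | 30 | 56% | 55% |
| +3% | 60 | 89% | 89% |

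Rough check: 0.56 × 0.025 = 0.014 under no effect, and 0.56 × 0.978 = 0.55 at +3%.

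**The case against.** The strongest reply is that Data interpretation can be read as a sequence. It opens with FMD being restored, says cutaneous tissue testing will confirm that reading, and only then turns to eNOS. On this view the regression is looked at only after an FMD gain, and the flat-FMD case has its own rule. That reading is possible, but the text does not state it. The eNOS rule carries its own condition, which is on eNOS, and nothing gives the lack-of-effect rule precedence. What stands is that one clarifying sentence would largely settle the matter.

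Second, the regression is offered as support for an interpretation about NO production, not as a test of the mean drug effect, and an association between eNOS changes and an NO-dependent readout is relevant to that. This stands. The slope is worth reporting, as an association.

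Third, the size rests on unknowns. The eNOS shift, r, and pooling to 60 are all assumptions. eNOS comes from skin biopsy and FMD from brachial ultrasound, and the plan offers no evidence that the two covary from visit to visit. At r = 0 the nominal rate holds. If eNOS does not rise on average, the eNOS condition keeps the rule near 2% even at r = 0.5. All of this stands, so the rates are illustrations.

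A reader might also infer that the plan would reject a mechanism that all subjects share equally. The slope does miss it: with a uniform +3% FMD and +0.75 SD eNOS and otherwise independent noise, it is positive in only 2–3% of trials. But the plan never treats a flat slope as evidence against the mechanism, and the planned mean tests of FMD and eNOS would each be positive in about 98% of 30-subject trials.

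Nor does the point extend to the planned analysis of the "relationship between changes in insulin-mediated vasodilation and insulin-sensitivity associated with active treatment". The plan attaches no decision rule to that regression.

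**Conclusion.** The concern holds for the eNOS support rule. Its slope does not depend on a drug effect shared by all analysed subjects, the rule requires no mean functional gain, and with unchanged vasodilation it conflicts with the rule that follows it. Those three statements rest on the text and on algebra. The algebra assumes a fitted intercept. If the two groups were pooled without a group term and only one responded, group means would enter the slope (positive in 15–22% of trials at n = 60, r = 0); the plan does not say whether it pools.

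The frequency is conditional: with no FMD effect, from about 2% at r = 0 to 78% at r = 0.5 with 30 subjects, given an eNOS rise of 0.75 SD.

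A reader might infer that 56% is an expected false-support rate, or that the trial's main result is in doubt. The documents support neither. They give no r, and this is a secondary mechanistic conclusion; the primary FMD comparison and the sample size are untouched. The correction is still worth making, because it can change a stated conclusion and costs only wording.

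**What to change.** In Data interpretation, replace the support sentence with a rule to this effect:

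- The regression counts as support only if eNOS phosphorylation is increased **and** the mean acipimox-minus-placebo change in the same function measure is significantly positive.
- If that mean change is not significantly positive, the regression gives no support. For unchanged vasodilation the lack-of-effect rule takes precedence, and a positive slope is reported only as a between-subject association.
- Even with a mean gain, the slope is associational. A non-significant slope is not evidence against the mechanism.

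Do not try to repair the rule by multiplying the slope by the mean eNOS change and calling the product the part of the FMD effect that tracks eNOS. At r = 0.4 the expected slope is 0.4 × 4 = 1.6 points per SD of eNOS, so the product averages 1.6 × 0.75 = 1.2 points whether the true FMD effect is 0 or −2. Under a uniform +3% response with r = 0 it averages about 0. It has the same fault as the slope.

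**Cost.** No new data and no new model. Support will be declared less often, but at a true +3% FMD gain and r = 0.4 the loss is about 1 point with 30 subjects and none with 60.

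**Limit.** The added condition does not separate a drug mechanism from visit-to-visit covariation when FMD truly improves. In that case support is still declared about as often as now (55% against 56% with 30 subjects at r = 0.4), so the associational caveat has to stay in the text.

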A whole-body hyperinsulinemic- euglycemic clamp will be created via an intravenous infusion of insulin. A primed constant insulin infusion of $80\text{mU}/\text{m}^2/\text{min}$ is started and continued for 120 minutes. This dose has been demonstrated to attain typical postprandial insulin concentrations, facilitating evaluation of both initial-phase and steady-state insulin-mediated vasodilation (65). Contralateral cubital vein glucose will be measured every 5 minutes to ensure a constant glucose concentration of 5.1 mmol (90 mg/dL). Adjusted dextrose 20% solution will be infused intravenously to maintain this concentration. Systemic glucose and insulin concentrations will be determined from the control arm cubital vein. Whole body insulin sensitivity will be quantified by determining M , (metabolized glucose) during the final 5 steady-state measurements. M will be calculated as the glucose infusion rate, adjusted according the method described by DeFronzo and colleagues (66).

Tissue Acquisition

Abnormalities in endothelium-dependent vasodilation have been demonstrated in humans in peripheral and coronary conduit arteries, peripheral and coronary resistance arterioles, and in skin microvessels of patients with diabetes (67-70). Therefore, we will biopsy easily accessible arm skin microvessels to determine the effects of each intervention on endothelial insulin signaling. The skin will be cleansed with betadine and draped to create a sterile field. Lidocaine 2% will be used to anesthetize a 1.2 cm ring in the arm around the biopsy site. A 6 mm bioptome will be used to obtain a

skin sample. The skin biopsy is marked for orientation and immediately frozen in liquid nitrogen and stored at –80 C for subsequent protein extraction for Western blot.

Tissue Analysis

The analyses of biopsy specimens will be performed in the laboratory of [name].

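### The Data interpretation rules, read literally, give opposite conclusions when flow-mediated dilation, insulin-mediated vasodilation and biopsy phosphorylation disagree

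*Combined protocol and SAP*

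**What the plan says.** Four statements under Data interpretation in the combined protocol and SAP matter here.

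- **Positive rule.** If FMD is restored on acipimox compared with placebo, "it will be interpreted that FFA impairs endothelial insulin signaling and decreases endothelium-dependent vasodilation". Insulin-mediated vasodilation is not part of the trigger. The next sentence adds: "This interpretation will be confirmed by cutaneous tissue testing".
- **eNOS rule.** If eNOS phosphorylation is higher after the intervention than after placebo, "it will be interpreted that improved activation of the PI3-kinase" pathway raises phosphorylation and nitric oxide production. This rule does not depend on the FMD result.
- **Null rule.** "If endothelium-dependent (flow-mediated) or insulin-mediated vasodilation remains similar despite an intervention (acipimox), it will be interpreted as a lack of effect". The conclusion is stated jointly, as a "lack of effect of the agent on endothelial-insulin signaling and vascular function".
- **Two-population rule.** "If the intervention improves vascular function in both subjects with the metabolic syndrome and healthy subjects, this will be interpreted as a generalized effect", that is, one not tied to the syndrome.

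Elsewhere, Statistical methods names FMD as primary ("The primary endpoint of change in flow-mediated" dilation). Tissue Acquisition says that the skin biopsy is taken "to determine the effects of each intervention on endothelial insulin signaling". The hypothesis under Study Procedures and Protocol lists conduit-vessel dilation, insulin-mediated dilation in resistance vessels, insulin sensitivity and AKT/eNOS phosphorylation in one joint sentence. The sample size calculation uses FMD only.

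**The concern.** The null rule has *or* in its trigger and *and* in its conclusion. Taken as written, one unchanged flow measure is enough to declare no effect on signaling and on vascular function together. The positive rule needs only FMD and leads the other way. The two are worded about different things (fatty acids in one, the agent in the other), but this does not separate them: inferring a fatty-acid effect from restored FMD requires that acipimox did something.

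The outcomes are distinct measurements: ultrasound of the brachial artery, plethysmography of forearm flow during the clamp, and tissue phosphorylation. They can disagree. Only FMD has a planned effect, SD and power, so a null on insulin-mediated vasodilation would be of unstated precision. At stake is which conclusion is reported after a discordant result. With both rules on paper, that choice would be made after the data are seen.

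**Working it through.** **1. The rules against each result pattern, read literally**

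| FMD | Insulin-mediated vasodilation | eNOS phosphorylation | Rules that fire | Outcome |
|---|---|---|---|---|
| restored | improved | any | positive | no conflict between the two flow rules |
| restored | similar | any | positive and null | opposite conclusions on signaling and vascular function |
| similar | improved | any | null | lack of effect on vascular function despite a resistance-vessel gain |
| similar | similar | not raised | null | no conflict |
| similar | similar | raised | null and eNOS | opposite conclusions on signaling |

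**2. Other readings of the null rule**

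- *Neither measure changes.* Row 2 is cured. Row 3 then has no rule of its own, because the two-population rule applies only when both populations improve. Row 5 still conflicts.
- *Endpoint by endpoint.* Row 2 can be reconciled for vascular function, but the stated conclusion joins signaling and vascular function whichever measure is unchanged. The wording would have to change for this reading to work.

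**3. How often a split would occur**

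The documents give no effect, SD or power for insulin-mediated vasodilation, so this cannot be computed. Purely as an illustration, take *similar* as non-significant, FMD power 0.978 (step 4) and independent outcomes. The chance of FMD significant and the other not is 0.978 × (1 − power of the other):

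- assumed power 0.9: 0.978 × 0.1 = 0.10
- assumed power 0.8: 0.978 × 0.2 = 0.20
- assumed power 0.5: 0.978 × 0.5 = 0.49

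These assumed powers have no source in the documents.

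**4. Secondary point: a null on FMD alone**

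Inputs from the sample size text and Table 2: 30 subjects per group, two-sided alpha 0.05, planned difference 3 points, SD 4% (Table 2 range 3.5% to 4.5%). The SD is taken as that of the within-subject difference.

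Standard error = 4/√30 = 0.730. Critical t on 29 df = 2.045. Noncentrality = true effect / 0.730. Power comes from the noncentral t.

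The plan's own figure first: at 3 points, noncentrality = 3/0.730 = 4.11 and power = 0.978, against 0.98 in Table 2. All nine cells of Table 2 reproduce to within 0.01. A two-sample formula gives 0.828 for that cell and does not fit, so the paired reading is the right one.

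Chance of a non-significant FMD result:

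| True effect (points) | SD 3.5% | SD 4% | SD 4.5% |
|---|---|---|---|
| 2 | 0.144 | 0.246 | 0.347 |
| 2.5 | 0.034 | 0.089 | 0.163 |
| 3 | 0.005 | 0.022 | 0.058 |

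If both groups were pooled (60 subjects, an assumption), the SD 4% figures at 2 and 3 points fall to 0.032 and 0.0001.

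In a simulation with 30 pairs, SD 4% and a true effect of 2 points, 24% of the non-significant results had an upper 95% limit of 3 points or more. Some such nulls would therefore not exclude the planned effect.

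**The case against.** The strongest reply is that this is loose drafting and that the intended meaning is recoverable. The hypothesis is one joint sentence, so failure of either flow component defeats it as a whole, which may explain the *or*. The sentence after the null rule ties nitroglycerin dilation to its own conclusion, smooth-muscle function, which suggests that endpoint-by-endpoint reading was intended. FMD is the only primary endpoint and has its own analysis.

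Part of this stands. The effects are hypothesized jointly, and the conflict depends on how *or* is read for rows 2 and 3. But defeating a joint hypothesis is not the same as showing lack of effect on every component, and the alternative readings are not what the text says. Row 5 survives the *neither* reading.

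A reader might infer that the null rule overrides a positive primary result. The documents do not support that: they give precedence to neither rule, so the conflict is unresolved and not settled against FMD. Nor is the tissue evidence discarded. In row 2 the positive rule fires, so tissue confirmation is in play, and in row 5 the eNOS rule still speaks. What remains in both rows is two statements that cannot both be reported.

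It is also fair to object that the type II error figures do not measure the split-result problem. They describe FMD alone, and the 25% applies to an effect smaller than any in Table 2. They support only the secondary point.

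**Conclusion.** The point holds as a matter of wording. Read literally, the rules contradict each other when FMD is restored and insulin-mediated vasodilation is not, and when both flow measures are null and eNOS phosphorylation rises. In the reverse flow split, the null rule denies an effect on vascular function despite a resistance-vessel gain. Nothing in the documents resolves these cases.

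The primary test, alpha and sample size are untouched. What is affected is the conclusion drawn from a discordant result, at a frequency that the documents do not allow one to compute. It should be fixed, but it does not threaten the primary analysis.

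The secondary point is minor. If *similar* means non-significant, with paired n = 30 and SD 4%, a false lack-of-effect statement on FMD has a chance of about 2% at the planned 3 points (0.5% to 6% over Table 2's SDs) and 25% at a true 2 points (14% to 35%). It would be wrong to infer from this that the trial is underpowered for its planned effect.

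**What to change.** Rewrite the null rule under Data interpretation so that each conclusion is limited to its own endpoint: FMD for conduit-artery function, insulin-mediated flow for resistance-vessel function, biopsy phosphorylation for signaling. Limit the signaling clause of the positive rule in the same way. Add a sentence that a null on one endpoint does not negate a positive result on another, so that discordant results are reported as discordant.

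As a smaller change, report a non-significant result as no difference detected, with its 95% CI. For FMD, say whether the interval excludes the planned 3 points. For insulin-mediated flow, where no planned effect is given, report the interval alone.

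The cost is a few sentences, with no new data, tests or subjects. The trial gives up a single whole-drug null statement, and some nulls will be reported as inconclusive.

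### The null rule turns vasodilation that stays similar into a claim of no effect, which is more than a null result can support, above all for insulin-mediated vasodilation, for which the trial was not sized

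*Combined protocol and SAP*

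**What the plan says.** The rule is in the combined protocol and SAP, Biostatistical Analysis, Data interpretation. Its condition is "If endothelium-dependent (flow-mediated) or insulin-mediated vasodilation remains similar despite an intervention (acipimox"), and its conclusion is that "it will be interpreted as a lack of effect of the agent on endothelial-insulin signaling and vascular function". Either endpoint is enough, because the two are joined by *or*.

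The sizing concerns FMD only: "Given the paired-design, the sample sizes have been calculated using estimates of the difference in flow-mediated, endothelium-dependent vasodilation after placebo and active treatment". The inputs are a difference "between the test agent and placebo of 3% with an estimated standard deviation of 4" per cent, and "With a 2-sided alpha error of 0.05 and a power of 90%, 30 subjects in each group of each protocol". Table 2 gives power for differences of 2.5%, 3.0% and 3.5% at SDs of 3.5%, 4.0% and 4.5%.

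Under Statistical methods, the primary endpoint is tested by repeated measures ANOVA and descriptive data are means with SDs. No confidence interval for the treatment difference is specified. Insulin-mediated vasodilation is part of the stated hypothesis, but no expected difference, SD or power for it appears anywhere.

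**The concern.** A test for a difference that comes out non-significant shows that a difference was not demonstrated. It does not show that there is none. To claim absence, the data must exclude a difference of stated size, and the rule asks for no such thing. It also has no label for a result that is neither positive nor clearly negative.

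The conclusion reaches beyond the endpoint tested. It covers endothelial insulin signaling, which the trial measures separately in skin biopsies and which this sentence does not consult.

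At stake is what the trial may conclude about its own hypothesis. FMD effects below the planned 3%, and forearm-flow effects of unknown size, could be declared absent on data that do not rule them out.

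**Working it through.** **Inputs.** From Sample size calculation and Table 2: 30 pairs, two-sided alpha 0.05, planned difference 3%, SD 4.0% (table range 3.5% to 4.5%). All FMD figures are absolute percentage points.

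**1. Reproduce Table 2.** Paired t-test power from the noncentral t, 29 df, noncentrality = difference × √30 / SD, taking the SD as that of the within-subject difference:

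| Difference | SD 3.5% | SD 4.0% | SD 4.5% |
|---|---|---|---|
| 2.5% | 0.966 (table .97) | 0.911 (.91) | 0.837 (.84) |
| 3.0% | 0.995 (.99) | 0.978 (.98) | 0.942 (.94) |
| 3.5% | 1.000 (1.0) | 0.996 (.99) | 0.984 (.98) |

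The table is therefore a calculation for 30 pairs. The text gives 90% power where the table gives .98 for the same inputs. That should be reconciled separately and does not change this point.

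**2. Precision.** The 95% half-width is h = t(0.975, n−1) × SD / √n. At SD 4.0%: 2.045 × 4 / 5.477 = 1.49. At SD 3.5% it is 1.31, and at SD 4.5% it is 1.68.

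**3. Largest effect compatible with a non-significant result.** Non-significance means the observed difference lies between −h and +h, so the upper limit cannot exceed 2h.

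| Pairs | SD 3.5% | SD 4.0% | SD 4.5% |
|---|---|---|---|
| 30 | 2.61 | 2.99 | 3.36 |
| 29 | 2.66 | 3.04 | 3.42 |

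- Break-even observed SD for excluding 3% with 30 pairs: 1.5 × 5.477 / 2.045 = 4.02%.
- Break-even for excluding 2.5%: 1.25 × 5.477 / 2.045 = 3.35%, below every SD in Table 2. Non-significance alone therefore does not guarantee exclusion of 2.5% at any tabulated SD.

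**4. How often the gap matters.** Simulation with 30 pairs, normal differences, the SD estimated in each trial and 400,000 trials per scenario:

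| True effect | Non-significant, SD 4.0% | Of all trials: non-significant and compatible with 3%, SD 4.0% | Same, SD 4.5% |
|---|---|---|---|
| 0 | 95% | 1% | 4% |
| 1.0% | 74% | 6% | 15% |
| 1.5% | 49% | 7% | 18% |
| 2.0% | 25% | 6% | 15% |
| 2.5% | 9% | 3% | 9% |

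At SD 3.5% the corresponding figure is at most about 1%. For compatibility with 2.5% at SD 4.0%, the figures are larger. With a true effect of 1.5%, 49% of the non-significant results still include 2.5%; with a true effect of 2.0%, 63% do.

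**5. Sensitivity to two assumptions.**

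- *Pooling both populations, 60 pairs.* h = 2.001 × 4 / 7.746 = 1.03, so the upper limit is at most 2.07 at SD 4.0%. The documents do not say whether the main comparison is pooled.
- *4% as the SD within each condition.* With a within-subject correlation of 0.25, the SD of the difference is 4 × √(2 × 0.75) = 4.90. Then h = 1.83 and the upper limit can reach 3.66. Table 2 does not support this reading.

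**6. Insulin-mediated vasodilation.** No equivalent calculation is possible, because the plan supplies no difference, SD or power for it.

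**The case against.** A reader might infer that an inconclusive FMD result would routinely be reported as negative. The documents do not support that. At exactly the planned 30 pairs and an observed SD of 4%, every non-significant FMD result already excludes 3%. An observed gain of 1.4% has an upper limit of about 1.4 + 1.49 = 2.9%, so it would be negative for the planned effect even under a stricter rule.

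A reader might also take the 49% and 25% chances of a null at true effects of 1.5% and 2.0% as the rate of misreporting. They are simply one minus power, for effects smaller than any in Table 2. At SD 4%, a check against 3% would relabel only about 7 of those 49 points and 6 of the 25. If both populations are pooled, the chances of a null fall to 18% and 3%.

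Third, the rule says similar, not non-significant. Equating the two is an inference.

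These objections stand and limit the FMD part. They leave three things untouched. The plan offers no other criterion for similar. Excluding 3% supports only the absence of an effect that large, not absence of effect on vascular function and signaling. And the argument about FMD precision does nothing for insulin-mediated vasodilation.

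**Conclusion.** The point holds in a limited form. The rule claims more than a null result can show, because it defines no criterion for similar, requires no exclusion of a stated difference and allows no inconclusive outcome. The case is strongest for insulin-mediated vasodilation, where nothing in the plan supports reading a null as absence.

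For FMD, protection against missing the planned 3% exists but is accidental and thin: a margin of 0.01 points at the planned inputs, lost with a slightly larger SD or one missing pair, and the plan states no allowance for dropout. It does not extend to smaller effects.

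The FMD figures assume that similar means not significant at two-sided 0.05, that Table 2's SD is that of the within-subject difference, and that each group of 30 is analysed on its own. With 60 pooled pairs the concern about 3% and 2.5% largely disappears at SD 4%, but effects up to about 2% would still not be excluded.

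**What to change.** Replace the lack-of-effect sentence with a statement, for each endpoint, limited to what its 95% confidence interval excludes.

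- **FMD:** conclude that there is no effect as large as the planned 3% only if the upper 95% limit of acipimox minus placebo is below 3%. Otherwise call a non-significant result inconclusive. Report the interval in every case, so that smaller effects are not declared absent.
- **Insulin-mediated vasodilation:** report the difference with its 95% interval, and draw no conclusion of no effect from non-significance.

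The cost is SAP wording. The intervals come from the planned models, and sample size, visits and treatment do not change. The downside is that some null results will be labelled inconclusive or stated more narrowly.
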